	
<math>CCS_{decomp}) > 0</math>. Superiority will be concluded if the posterior probability is at least equal to 0.95.
 
Objective 4: (real conditions of use): The following hypotheses will be tested in order to evaluate whether or not coflex® device performance is clinically inferior in the PAS population compared to the IDE population using a non-inferiority <math>\delta=-0.1175</math>. The following hypotheses will be tested.
 
Ho: <math>CCS_{PAS} \leq CCS_{IDE} - 0.1175</math>
 
Ha: <math>CCS_{PAS} > CCS_{IDE} - 0.1175</math>.
 
Non-inferiority of coflex performance in the PAS population will be concluded if the posterior probability that (<math>CCS_{PAS} > CCS_{IDE} - 0.1175</math>) is at least 0.95.
 
Sample Size Analysis Details concerning the Bayesian simulations for this study were previously reviewed and are included in Bayesian Simulations Memo, Version 4.1, May 5, 2015.
 
Objective 1: (5-year superiority) These Simulations were used to evaluate the power and type 1 error for determining superiority of coflex® in conjunction with surgical decompression relative to surgical decompression alone at Month 60. For the purpose of these simulations it was assumed that the Month 60 success rate would be 0.57 for coflex®. A posterior probability threshold of at least 0.95 was selected. Power was found to be equal to 83% if the true superiority margin is 12.5%. If the true superiority margin is only 10%, then power to conclude superiority is reduced to 65%. Type 1 error was determined through simulation by assuming that the probabilities of Month 60 success were equal to 0.57 for both device groups. The estimated type 1 error rate is equal to 0.037(SD=0.0011) based on an average of 10 identical simulations with varying randomization seeds.
 
Objective 2: (2-year non-inferiority) Bayesian simulations were performed to evaluate the operating characteristics for testing the Objective 1 hypothesis non-inferiority hypothesis. In the pivotal IDE study, 135 of 204 patients (66.2%) achieved Month 24 CCS. These results were used to define the prior distribution for coflex in conjunction with surgical decompression as beta (135.5, 69.5) since the distribution prior to the IDE trial was specified as beta (0.5, 0.5). This Jeffries non-informative prior was assumed for patients undergoing decompression alone. A non-inferiority margin of -0.10 is specified. Non-inferiority will be concluded if the Bayesian posterior probability that (<math>CCS_{coflex+decomp} - CCS_{decomp}) > -0.10</math> is at least equal to 0.95. When evaluating

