### 4.2. Number of Subjects

The numbers of patients to be enrolled is 150 patients per group (300 total). This total will be increased by 15% to account for loss-to-follow-up. The sample sizes were increased by an additional 20% in control group and 5% in the study device group to account for trimming of control patients and possible trimming of study device patients during the propensity score design. Therefore, the total enrolled will be 186 coflex patients and 220 decompression control patients for a total enrollment of 406.

Patients will be enrolled into one of the treatment groups (Group A, without additional implant, Group B, with coflex® Interlaminar Technology).

Recruitment of about 5 patients per month is expected. Each site will be required to enroll at least 5 patients.

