## 7.3. Objective 1: 5-Year Superiority

Five-year superiority will be evaluated by testing the hypothesis that the coflex device in conjunction with surgical decompression is superior to decompression alone at five years. This objective will be met by testing the following superiority hypotheses:

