## 7.11. Handling of Missing Data for Primary CCS Endpoints

### 7.11.1. Bayesian Multiple Imputation

To best preserve an intent-to-treat analysis, the testing of the primary Month 60 superiority hypothesis (Objective 1) will be done on the ITT-PS selected analysis set. Those subjects who withdraw, or who are lost to follow-up (LT FU) after enrollment will be included in the analysis using a modification of Bayesian multiple imputation to accommodate the PS subclass design. This analysis will be the primary analysis, but recognizing that there is no way, statistically, to handle these subjects without possibly introducing bias, a tipping point analysis will be also be conducted. For comparison purposes, a completers analysis will also be performed. The following describes the method. A similar method will be applied to analyses for other objectives.

In general, Bayesian Multiple Imputation (MI) may be employed to impute the expected status at Month 60 for patients who have not completed follow-up and have not been identified as “terminal failures”. Terminal failures include any event which is counted as a CCS failure no matter what happens after such an event occurs such as a secondary surgical invention. The imputation algorithm uses a beta-binomial distribution to model the transition probabilities from the outcome at month  $j$  to that at month 60, separately for the treatment and control groups. Specifically, the probability of a success for a subject in treatment group  $t$ , with last follow-up  $j$  and last follow-up value  $r$  can be described using a beta distribution:

$$\Pi_{p,t,j,r} \sim \beta(1 + S_{p,t,j,r}, 1 + F_{p,t,j,r})$$

Where  $p$  = propensity score subclass = {1, 2, 3, 4, 5}

$t$  = treatment group = {coflex=S, Decompression=D}

$j$  = follow-up time = {3, 6, 12, 24, 36, 48}

$r$  = success or failure status at time  $j$  = {1=success, 0=failure}

$\Pi_{p,t,j,r}$  = Month 60 success probability for subjects in subclass  $p$ , in treatment group  $t$ , who were successes ( $r=1$ ) or failures ( $r=0$ ) at follow-up time  $j$ .

$S_{p,t,j,r}$  = Number of Month 60 successes for subjects in subclass  $p$ , in treatment group  $t$ , who were successes ( $r=1$ ) or failures ( $r=0$ ) at follow-up time  $j$ .

 Guidance for Industry and FDA Staff Clinical Data Presentations for Orthopedic Device Applications Document issued on: December 2, 2004.

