$F_{p,t,j,r}$  = Number of Month 60 failures for subjects in subclass p, in treatment group t, who were successes (r=1) or failures (r=0) at follow-up time j.

Note that these transition beta distributions assume non-informative prior distributions to allow only the observed data to impact on the multiple imputations (i.e., all a and b are set to 1). Subsequently, the informative prior on the study device group is applied to determine the posterior distribution of non-inferiority.

In order to implement the Bayesian Multiple Imputation algorithm, the following steps will be used.

1. For each patient that has not completed follow-up, a value  $\pi_i$  is randomly chosen from  $\Pi_{p,t,j,r} \sim \beta(1 + S_{p,t,j,r}, 1 + F_{p,t,j,r})$  corresponding to their PS subclass, treatment group, and success-failure status at their last known follow-up; this value represents the probability that the subject is a success at 60-months.
2. Using this randomly chosen  $\pi_i$ , the patient is then assigned a success (1) or failure (0) from a random draw of the binomial distribution  $Bin(n, p)$  with  $n = 1$  and  $p = \pi_i$ .
3. Steps 1-2 are repeated for all subjects with incomplete follow-up, separately for each treatment group and propensity score subclass.
4. Using the resulting completed datasets (containing both observed and imputed values at month 60), the PS-adjusted total number of successes ( $S_t$ ) and failures ( $F_t$ ) at month 60 are calculated for each treatment group using the average of PS subclasses as described above. The probability of success for each treatment is then chosen randomly from the resulting posterior beta distributions incorporating the informative prior in the study device group and the non-informative prior for controls. The distribution of the difference in success probabilities is therefore:

$$\pi_S - \pi_D \sim \beta(82.1 + S_t, 62.1 + F_t) - \beta(1 + S_D, 1 + F_D)$$

5. Step 4 is repeated ( $n = 10,000$  times), to obtain the posterior distribution of the differences in treatment success ( $\pi_S - \pi_D$ ), and the posterior probability of non-inferiority is calculated as the proportion of times that  $\pi_S - \pi_D \geq -\delta$ .
6. To complete the multiple imputation and obtain the final posterior non-inferiority probabilities, steps 1-5 are repeated 20 times and the final posterior probability is determined as the average of the 20 multiple imputations.

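### The primary Objective 1 decision averages only 20 imputations with no fixed seed, so the seed can decide a borderline result (converged posterior about 0.94 to 0.96)

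*Combined protocol and SAP*

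**What the plan says.** Section 7.3 tests whether "the coflex device in conjunction with surgical decompression is superior to decompression alone at five years". The synopsis, in the sample size text for Objective 1, states: "A posterior probability threshold of at least 0.95 was selected". Section 7.3 applies the same cut-off to the final analysis.

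Section 7.11.1 says of the multiple imputation analysis: "This analysis will be the primary analysis, but recognizing that there is no way, statistically, to handle these subjects without possibly introducing bias". It imputes Month 60 status "for patients who have not completed follow-up and have not been identified as" terminal failures. Steps 1 to 3 draw a success probability and then a success or failure for each such patient. Steps 4 and 5 take 10,000 draws from the two beta posteriors "to obtain the posterior distribution of the differences in treatment success". Step 6 then closes the procedure: "steps 1-5 are repeated 20 times and the final posterior probability is determined as the average of the 20 multiple imputations".

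On the amount of missing data, section 4.2 gives only a planning allowance: "This total will be increased by 15% to account for loss-to-follow-up".

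Neither section 7.11 nor the software section (7.20) gives a random seed, a limit on Monte Carlo error or a rule for adding imputations. Seeds are mentioned only for the design simulations, in section 7.7.1 and the matching synopsis text.

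**The concern.** The decision compares one number with a hard cut-off, and that number is itself a Monte Carlo estimate. It has two sources of random error. One is the draw from the posterior within each completed data set, which 10,000 draws make negligible. The other is the random completion of the missing outcomes, which is averaged over only 20 values. The computing effort is spent on the source that needs it least.

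If the second error is not small compared with the distance of the result from 0.95, the same locked data can give either conclusion depending on the seed. Without a pre-specified seed, a borderline primary result could not be reproduced by someone else and could raise the suspicion that the seed was chosen after the fact.

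**Working it through.** **Inputs from the protocol.** 150 evaluable per group, 15% loss allowance, 186 coflex and 220 controls enrolled (4.2). Coflex Month 60 success 0.57 and coflex prior beta(82.1, 62.1) (7.7.1). Control prior beta(1, 1), 10,000 draws and 20 imputations (7.11.1). Threshold 0.95 (7.3). Steps 5 and 6 speak of non-inferiority and a margin, but Objective 1 is a superiority test, so the margin was set to 0.

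**Reproducing the plan's figures.** Exact beta-binomial enumeration at 150 per group, with beta(0.5, 0.5) or beta(1, 1) for control:

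| Quantity | Section 7.7.1 | Recomputed |
|---|---|---|
| Power, 12.5-point difference | 83% | 82.2 to 82.3% |
| Power, 10-point difference | 65% | 64.6 to 64.7% |
| Type 1 error | 0.037 | 0.035 to 0.036 |

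The model therefore represents the stated design.

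**Numbers for the imputation step.** 150/0.85 = 176 per arm. Planned trimming leads to the same place: 186 × 0.95 = 177 and 220 × 0.80 = 176. At 15%, 0.15 × 176 = 26 outcomes per arm are imputed. This is an upper case, because terminal failures are not imputed.

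**Assumptions not in the protocol.** Five subclasses; Month 60 success with probability 0.85 after a last-visit success and 0.20 after a last-visit failure. The alternative case has an uninformative last status. The imputed fraction was varied over 5%, 10% and 15%.

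**Within-imputation error.** √(0.95 × 0.05 / 10,000 / 20) = 0.0005, which is negligible.

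**Between-imputation error near 0.95.** Seed standard error = SD/√20:

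| Imputed | SD between imputations | Standard error, 20 | Standard error, 1,000 |
|---|---|---|---|
| 15%, informative last status | 0.0293 | 0.0066 | 0.0009 |
| 15%, uninformative last status | 0.0360 | 0.0081 | 0.0011 |
| 10% | 0.0245 | 0.0055 | 0.0008 |
| 5% | 0.0173 | 0.0039 | 0.0006 |

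With other transition probabilities (0.7 to 0.8 after success, 0.2 to 0.3 after failure) the SD was 0.027 to 0.035, so the standard error was again 0.006 to 0.008.

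**Fixed data sets, 400 seeds each, 15% imputed.** Share of seeds reaching 0.95:

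| Converged posterior | 20 imputations | 1,000 imputations |
|---|---|---|
| 0.935 | 1% | 0% |
| 0.940 | 11% | 0% |
| 0.945 | 26% | 0% |
| 0.950 | 49% | 40% |
| 0.955 | 77% | 100% |
| 0.960 | 95% | 100% |
| 0.965 | 99.8% | 100% |

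At 0.950 the central 95% of the 20-imputation results ran from 0.938 to 0.961.

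**How often a trial lands there.** 1,500 simulated trials per scenario. A trial counts as undecided if its chance of passing, over seeds, is between 5% and 95%:

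| Scenario | Undecided | Two seeds disagree |
|---|---|---|
| 12.5 points, 15% imputed | 6.2 to 6.7% | 2.2 to 2.3% |
| 10 points, 15% imputed | 7.6% | 2.6% |
| Null, 15% imputed | 1.9% | 0.6% |
| 12.5 points, 10% imputed | 4.4% | 1.4% |
| 12.5 points, 5% imputed | 2.4% | 0.9% |

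With 1,000 imputations, disagreement at 12.5 points and 15% imputed falls to 0.3%.

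**Error rates.** A separate simulation with 3,000 trials per scenario and a normal approximation to the posterior gave a null pass rate of 3.9% with 20 imputations and 3.7% with 1,000. Power was 84.8% and 85.0%. Both differences are within simulation noise.

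**The case against.** The strongest reply is that the problem is rare and leaves the operating characteristics alone. That stands. Quoting only the seed shares for data sets close to 0.95 would misstate the risk: in about 97 to 98% of trials at the differences studied, two seeds would agree.

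A reader might go further than the documents allow in three ways.

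- *That the type 1 error is inflated.* The seed noise moves results in both directions, and no change in error rate was visible.
- *That about 53 outcomes will be imputed.* That count applies 15% to everyone left after trimming. Section 4.2 gives 15% as an allowance, not an observed rate, and section 7.11.1 does not impute terminal failures. A patient with a reoperation or with two or more series of injections is a known failure even if later lost (5.1.2, 5.1.3).
- *That the same figures hold for Objectives 2 to 4.* Section 7.11.1 says only that a similar method will be used. Month 24 comes three years earlier, and any lumbar injection before it is already a failure. Objectives 2 and 3 use a beta(135.5, 69.5) prior (7.7.2, 7.7.3). Objective 4 uses non-informative priors and compares with the earlier pivotal trial rather than with controls (7.7.4). The effect was not computed for these.

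It can also be said that a fixed seed alone would make the result reproducible. It would, but the fixed-seed answer could still lie on the other side of 0.95 from the converged one. The tipping-point analysis (7.11.2) and the completers analysis would show that a borderline result is fragile. They address assumptions about missingness, however, and do not remove the seed noise from the primary number.

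**Conclusion.** The point holds for borderline results. With up to 15% of outcomes imputed, the 20-imputation average carries a seed standard error of about 0.006 to 0.008 near the threshold, and about 0.004 at 5%. The seed can decide Objective 1 when the converged posterior is about 0.94 to 0.96; outside that band it has almost no influence. This is a limited weakness in reproducibility and accuracy, not a flaw in the error rates. The sizes rest on assumed transition probabilities, but the standard error changed little across the cases tried. The imputed fraction matters more, and it will not be known until follow-up ends. The change is worth making because the plan leaves a primary decision open to chance for no saving.

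**What to change.** In section 7.11.1, step 6:

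- replace 20 with at least 1,000 imputations, which gives a seed standard error of about 0.001;
- pre-specify the random seed;
- report the Monte Carlo standard error beside the posterior probability;
- add imputations if the result is within about two standard errors of 0.95. This rule is needed because a converged value almost exactly at 0.95 stays undecided even at 1,000. A stated maximum would close the rule; 5,000 imputations bring the standard error to 0.0004 to 0.0005.

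Apply the same setting wherever the similar method is used for Objectives 2 to 4. The change touches no endpoint, estimand or sample size. It costs a short edit to the analysis plan and minutes of computing.

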### 7.11.2. Tipping Point Analysis for Primary Outcomes

A tipping point sensitivity analysis will be conducted in which missing values in each group are separately assumed to be either successes or failures. Treatment group differences will be computed based on all possible combinations of assigning success or failure to the primary overall success endpoint to the patients in the two groups. For example, one scenario will be that all missing coflex device observations are failures and all missing decompression alone observations are successes. The next scenario would have one success and the remaining missing values as failure for coflex and all missing controls as successes. For each objective, the Bayesian posterior probability will be determined. These results will be plotted using a dot plot with the number of missing assumed as failures for coflex in conjunction with surgical decompression on the x-axis and the number of missing assumed as failures for controls on the Y-axis. The dots will be color

coded to indicate whether or not the primary statistical conclusion changes under each individual scenario. If the fraction of scenarios in which the statistical conclusion changes is small, the primary results will have been shown to be robust against assumptions concerning missingness.

### **7.11.3. Plan for Missing Baseline Covariates**

Since data for the study device patients and control group patients will be prospectively collected, it is anticipated that there will be very little, if any missing covariate data. If there are some missing covariate values, and these represent a very small percentage of the total amount of covariate information overall and for every subject, then the missing data will be imputed using a single imputation strategy employing multiple linear regression for continuous covariates and multiple logistic regression for dichotomous covariates. These models will include all other variables to be used in the PS modeling. If there is more than a trivial amount of missing covariate data, then a multiple imputation strategy will be used. The multiple imputation strategy will involve determining PS scores for each of 20 MI completed data sets and then using the average PS score for each step in the PS subclassification identification strategy. If MI is needed, it is likely that the missing value pattern will not be monotonic. Therefore, a fully conditional specification (FCS) approach will be utilized as implemented in SAS Proc MI. Details regarding the imputation strategy, if needed, will be included in the PS Results Memo to be submitted for FDA review prior to unblinding outcomes to the outcomes-blinded statistician responsible for determining the PS subclasses.

## **7.12. Sub Group Analysis**

Primary endpoints and selected secondary endpoints will be subjected to stratified analyses in order to evaluate poolability and heterogeneity of treatment group differences. Stratifications will include age (<65 vs  $\geq$  65 years), gender, body mass index (<30 vs  $\geq$  30 k/m^2) and other clinically relevant factors.

## **7.13. Device Survival through 24 months**

Kaplan-Meier survival analysis will be used to characterize and compare treatment failure time distributions between. Life-tables will be tabulated indicating the number of “failures” and the number of “at-risk” patients over time for each endpoint, separately by device group.

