## SYNOPSIS OF THE CLINICAL INVESTIGATION PLAN

SPONSOR	Paradigm Spine LLC
NAME OF STUDY PRODUCT	coflex® Interlaminar Technology
Class of Medical Device	Class III
STUDY TITLE	A 2 and 5 year comparative evaluation of clinical outcomes in the treatment of degenerative spinal stenosis with concomitant low back pain by decompression with and without additional stabilization using the coflex® Interlaminar Technology for FDA Real Conditions of Use Study.
INT. PROJECT NUMBER	PAS003
PROJECT MANAGER	TBD
CRO	Musculoskeletal Clinical Regulatory Advisers, LLC CRO Washington, DC
PRINCIPAL INVESTIGATOR and RELATED STUDY SITE	TBD
FURTHER INVESTIGATORS and RELATED STUDY SITES	TBD
RELEVANT LITERATURE	
Stucki, Gerald, MD. et al., Measurement Properties of a Self-Administered Outcome Measure in Lumbar Spinal Stenosis. Spine. Vol. 21(7). pp. 796-803.
 
Pratt RK, MA, FRCS, et al. The Reliability of the Shuttle Walking Test, the Swiss Spinal Stenosis Questionnaire, the Oxford Spinal Stenosis Score and the Oswestry Disability Index in the Assessment of Patients with Lumbar Spinal Stenosis. Spine Vol. 27 (1) pp. 84-91.
 
Fairbank J.C.T., The Oswestry Disability Index, Spine Volume 25, Number 22, pp 2940-2953, 2000^11

DURATION OF THE CLINICAL INVESTIGATION	
Per Patient: 60 months
 
Recruitment 36 months
 
Total: 96 months

OBJECTIVES	Meet FDA mandated post-approval Real Conditions of Use evaluation

METHODOLOGY and STUDY DESIGN	
Prospective, multicenter, concurrently enrolled, propensity score controlled through Month 60.
 
Up to 10 treatment (coflex) sites
 
Up to 10 control (decompression) sites

NUMBER OF PATIENTS	
150 per group (300 total) plus 15% to account for LTF in both; plus 20% in control group and 5% in the study device group to account for trimming of control patients and possible trimming of study device patients during the propensity score design. Therefore, the total enrolled will be 186 coflex patients and 220 decompression control patients.

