## CLINICAL INVESTIGATION PLAN

### 1. Background Information

The treatment of degenerative spinal stenosis is not adequately appreciated in the literature and prospective controlled clinical studies are lacking.

Non-controlled, retrospective studies have shown very different and inhomogeneous results and allow only limited conclusions regarding clinically occurring lower back pain.

Caputy et al. (1992) found in a five-year follow-up period after decompression (n=88) 27% failures, that showed recurrent neurologies and persisting low back pain. Katz et al. (1996) found in a 7-10 years follow-up period (n=88) 20 patients that had to undergo further surgery. 33% complained about severe back pain and 53% showed a severe limitation of walking distance. A large study in Finland with 438 patients could show retrospectively that 38% of the patients evaluated the result of the surgery after decompression as bad or very bad (Airaksinen et al. 1997). Iguchi published in 2000 a series of 37 patients that were all treated surgically more than 10 years earlier. It could be shown that low back pain was clearly harder to treat than leg pain or walking distance. 44% of the patients evaluated the result as only acceptable to bad.

Until now no guidelines for therapeutic treatment are defined. With isolated decompression the main neurological findings are treated. Accompanying back pain is comparably harder to treat.

The coflex® Interlaminar Technology - manufactured by Paradigm Spine - is intended for use as a permanent implant between the lamina of 1 or 2 lumbar motion segments in the treatment of moderate to severe lumbar spinal stenosis. The device is specifically designed to provide stabilization without fusion in cases of stenosis with or without facet joint hypertrophy, subarticular recess stenosis or foraminal stenosis. It is restricted for use to one or two levels in the region of L1 – L5.

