### 3. Study Objectives and Endpoints

#### 3.1. Study Objectives

##### **Objective 1:**

The first objective of this trial is to evaluate 5-year clinical status of patients implanted with the coflex® device in conjunction with surgical decompression relative to decompression alone. This objective will be accomplished by a Bayesian test of superiority using Month 60 composite clinical success. The composite primary endpoint for this objective is in three parts:

1. At least a 15 point improvement relative to pretreatment baseline in the Oswestry Disability Index (ODI, range 0-100);
2. No reoperations, revisions, removals, or supplemental fixation at the index level(s);
3. No  $\geq 2$  injections or series of injections for any lumbar level\*\*, or nerve block procedures performed to treat spinal stenosis at any lumbar level(s) or a single injection within 12 months of the 5 year endpoint.

\*\* A series of injections is considered 2-3 injections performed between 24-hour and one week intervals designed to treat a single pain event. Secondary injections performed due to patient demand or recurrence of symptoms following the initial injection are considered separate injections and would constitute a study failure.

Additionally, a sensitivity analysis will be performed with the condition where lumbar injections occurring at any time between surgery and Month 60 will be considered a treatment failure.

A lumbar injection is defined as any deep injection into the spine, typically under image-guidance, of steroids and/or other pharmacologic agents (e.g., facet injections or epidural injections by the transforaminal, interlaminar, or caudal routes). Other types of injections are not treatment failures such as trigger point injections, intramuscular injection for systemic administration of steroids, dry-needling, prolotherapy, or acupuncture, but a sensitivity analysis will be performed including all types of injections.

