- Spontaneous fusion (unplanned, self-generated fusion of the vertebra)
- The spine may undergo unfavorable changes or deterioration at the operated level(s) and/or the levels above and below including loss of proper spinal curvature, correction, height, and/or reduction, or malalignment, which may require another surgery

Adverse events that are associated with coflex implant:

- Implant malposition or orientation (the implant could be improperly positioned)
- Allergies to implant materials (possible allergic reaction to the metal)

- Possible wear debris (there may be some wearing of the implant material against bone or another part of the implant that creates very small particles; it is possible that these particles may eventually cause the local tissues such as bone, nerves and nearby soft tissue to respond badly)
- Impantation of the study device at the wrong level of the spine
- Fracture of the vertebrae, spinous process, or other damage to bony structures during or after surgery
- Implant may loosen, deform (permanently change shape), break, fatigue (wear out), or move which may require another surgery to correct the problem and/or remove the implant
- Instruments also may break or malfunction in use, which may cause damage to the operative site or adjacent structures

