## 7.18. Analysis of Safety

### 7.18.1. Adverse Events

Assessment of the safety of the coflex implant will be based on the incidence and seriousness of adverse events associated with the treatment.

Adverse event rates will be summarized by type of AE and for specific AEs in two ways: 1) per patient using counts and percentages and 2) by event, summarizing event counts by visit interval over time. Device and procedure related events will be summarized by seriousness. Events listings will be provided that include details such as relatedness, severity, onset and resolution status will be provide for all events and for relevant subsets of events such as serious events and related events.

All adverse events (AE) will be listed according to ICH guidelines. Additional tables presenting a survey of the incidence rates by treatment groups will be drawn up for the following classifications and items:

- Premature Termination, Serious Adverse Events and Causal Relationship
- Separate Presentation of Serious Adverse Events

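### The only time-to-event analysis is headed 24 months, so no censoring-adjusted separate estimate of secondary surgery, device removal or implant breakage is planned for Months 24 to 60

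*Combined protocol and SAP*

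**What the plan says.** - **Time-to-event analysis.** Section 7.13 is headed "Device Survival through 24 months" in the body and in the table of contents. Its text says that Kaplan-Meier analysis "will be used to characterize and compare treatment failure time distributions between", and the sentence stops there without naming what is compared. Life-tables are to give failures and numbers at risk for "patients over time for each endpoint, separately by device group". The endpoints are not listed, and the body states no end month. No other section plans a survival curve or life-table.
- **Follow-up.** The synopsis gives "Per Patient: 60 months". Objective 1 (3.1) is to "evaluate 5-year clinical status of patients implanted with the coflex" device relative to decompression alone. Patients who have secondary surgery stay in follow-up (5.1.2). Adverse events and pain management, including injections, are recorded through Visit 8 at Month 60 (4.7.8, 4.8.10).
- **Known late risks.** The device risk list in 6.1 includes "Implant may loosen, deform (permanently change shape), break, fatigue (wear out), or move which may require another surgery".
- **Safety summaries.** Section 6 lists implant breakage, revisions and additional stabilizations as safety items but gives no estimator. Section 7.18.1 summarizes adverse events per patient, as counts and percentages, and "by event, summarizing event counts by visit interval over time".
- **Month 60 primary endpoint.** Reoperations, revisions, removals and supplemental fixation at the index level are failures in the Month 60 CCS (5.1). Section 7.11.1 treats secondary surgery as a terminal failure and multiply imputes Month 60 status for patients lost to follow-up. Section 7.11.2 adds a tipping-point analysis.

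**The concern.** Read as headed, 7.13 leaves three of the five follow-up years outside the only analysis that accounts for time at risk. Those years include the period in which fatigue or loosening of an implant could lead to further surgery.

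The composite does not fill this gap. It combines ODI response, surgery and injections at one time point, so it gives no reoperation or removal rate and no timing. Implant breakage is not a CCS component unless it leads to surgery. Section 7.11 covers the primary CCS endpoints and does not extend to the safety summaries.

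What remains for late device failure as an outcome in its own right is a crude percentage. If its denominator is everyone treated, it understates cumulative risk when patients are lost. If loss differs between arms, it can suggest a difference that is not there. Differential loss is plausible because each site enrolls only one arm (4.6).

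**Working it through.** **1. The plan's own figures.** No power or sample size is attached to 7.13, so the nearest check is the loss allowance in 4.2 (150 per group, 15% loss, then 5% coflex or 20% control trimming):

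- coflex: 150 / 0.85 / 0.95 = 185.8, stated 186
- control: 150 / 0.85 / 0.80 = 220.6, stated 220

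The enrollment figures reproduce, and 15% is used as the fraction of patients lost. Objective 1 also reproduces by simulation with 150 per group and the beta(82.1, 62.1) prior. Power is 82.6% against a stated 83% at a 12.5-point difference, and 64.7% against 65% at 10 points. Type 1 error is 0.036 to 0.037 against 0.037. None of these figures depends on the horizon of 7.13.

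**2. Formulas for the illustration.** The documents give no 60-month reoperation or breakage rate, so the true 60-month risk F is assumed, as are constant event and loss hazards. L is the fraction lost by Month 60.

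- event hazard h = −ln(1 − F) / 60; loss hazard g = −ln(1 − L) / 60
- risk by Month 24 = 1 − exp(−24h)
- share of events after Month 24 = (F − risk by Month 24) / F
- crude 60-month proportion = h / (h + g) × [1 − exp(−60(h + g))]

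**3. Worked case, F = 20%, L = 15%.** 60h = 0.2231 and 60g = 0.1625. Risk by Month 24 = 1 − exp(−0.4 × 0.2231) = 8.5%, so (20 − 8.5) / 20 = 57% of events come later. Crude proportion = 0.2231 / 0.3857 × (1 − 0.80 × 0.85) = 0.5786 × 0.32 = 18.5%.

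**4. Range.**

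| True 60-month risk | Risk by Month 24 | Share after Month 24 | Crude, 15% loss (planned) | Crude, 30% loss (assumed) |
|---|---|---|---|---|
| 10% | 4.1% | 59% | 9.2% | 8.4% |
| 15% | 6.3% | 58% | 13.9% | 12.7% |
| 20% | 8.5% | 57% | 18.5% | 16.9% |
| 25% | 10.9% | 57% | 23.2% | 21.2% |

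The shortfall is 0.8 to 1.8 points at the planned loss and 1.6 to 3.8 points at 30%.

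**5. Unequal loss, same true risk of 20% in both arms.** Loss of 5% against 25% gives crude rates of 19.5% and 17.5%, a spurious gap of 2.0 points. Loss of 10% against 30% gives 19.0% and 16.9%, a gap of 2.1 points. For scale, the standard error of a difference at 20% with 150 per arm is √(2 × 0.20 × 0.80 / 150) = 4.6 points.

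**The case against.** A reader might infer that reoperations and removals after Month 24 are reported only as crude counts that ignore loss to follow-up. The documents do not support that. These events are failures in the Month 60 CCS, are carried forward once they occur, and sit in an analysis with imputation within arm and propensity score (PS) subclass and a tipping-point check. CCS is also determined at Months 36 and 48 (3.2.1, 5.1.3), and follow-up compliance is reported by group over time (7.10). A reader might also object to unequal visit intervals, but every scheduled interval after Month 24 is 12 months (4.8.10).

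Other points on the plan's side:

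- **The 24-month limit rests on a heading.** This is true, and the body sets no end month. But then the horizon is unclear and the sentence is still unfinished, so 7.13 needs rewriting on either reading.
- **Treatment Failure is a two-year concept.** For Objectives 2 and 3 it runs to the exact 2-year anniversary, and the CCS injection rule changes after Month 24. This stands: simply running the treatment-failure curve longer would mix definitions. It does not affect surgery or removal, whose definitions in 5.1.2 are constant, and injections can be analyzed as a separate event.
- **The sizes are assumed and small.** This also stands. With constant hazards the late share is close to 36/60 = 60% almost by construction. The background figure of "20 patients that had to undergo further surgery" comes from 7 to 10 years after decompression and cannot supply a 60-month device rate.
- **Kaplan-Meier is not a full cure.** It assumes non-informative censoring, so it would not remove all bias from site-driven differential loss.

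**Conclusion.** The point holds in a limited form. No censoring-adjusted, separate estimate of secondary surgery, device removal or revision, or implant breakage is specified for Months 24 to 60. Reoperations and removals do enter the imputed Month 60 composite, but that yields neither their rate nor their timing, and breakage without surgery does not enter it at all.

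The numerical bias of the crude percentages is modest: about 1.5 points for a true 20% risk at the planned 15% loss, and about 2 points between arms under the unequal-loss scenarios shown. These figures rest on assumed risks, constant hazards and, for the between-arm gap, assumed loss rates. The stronger reason to act is that the trial would follow patients for five years without a planned 5-year device-survival estimate. Section 7.13 carries no hypothesis or decision rule, so no primary conclusion is affected.

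**What to change.** Retitle 7.13 to run through Month 60, complete the unfinished sentence, and specify Kaplan-Meier curves and life-tables to Month 60 by arm, averaged over PS subclasses as in 7.1, for:

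1. any secondary surgery at the index level;
2. device removal or revision (coflex arm);
3. implant breakage (coflex arm);
4. first lumbar injection, defined as an event in its own right because the CCS injection rule changes after Month 24.

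Censor at last contact, state how death is handled (for example as a competing event), and keep Month 24 as a landmark on the same curves. Present the results alongside the 7.18 counts.

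The cost is SAP wording and a little more programming, largely on event data that the plan already collects. Late failure rates may look slightly less favorable than crude percentages. Power, sample size and the primary analyses are unchanged.
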